## **1.5 Nivolumab Activity and Pharmacokinetic Profile**

### **1.5.1. Introduction**

Nivolumab (also referred to as BMS-936558, MDX1106, or ONO-4538) is a human monoclonal antibody (HuMAb; immunoglobulin G4 [IgG4]-S228P) that targets the programmed death-1 (PD-1) cluster of differentiation 279 (CD279) cell surface membrane receptor. PD-1 is a negative regulatory molecule expressed by activated T and B lymphocytes. Binding of PD-1 to its ligands, programmed death–ligands 1 (PD-L1) and 2 (PD-L2), results in the down-regulation of lymphocyte activation. Inhibition of the interaction between PD-1 and its ligands promotes immune responses and antigen-specific T-cell responses to both foreign antigens as well as self-antigens. Nivolumab is expressed in Chinese hamster ovary (CHO) cells and is produced using standard mammalian cell cultivation and chromatographic purification technologies. The clinical study product is a sterile solution for parenteral administration. OPDIVO™ (nivolumab) is approved for the treatment of several types of cancer in multiple regions including the United States (US, Dec-2014), the European Union (EU, Jun-2015), and Japan (Jul-2014). Nivolumab is also being investigated in various other types of cancer as monotherapy or in combination with other therapies, and as single-dose monotherapy for the treatment of sepsis.

### **1.5.2. Nonclinical Studies**

Nivolumab has been shown to bind specifically to the human PD-1 receptor and not to related members of the CD28 family. Nivolumab inhibits the interaction of PD-1 with its ligands, PD-L1 and PD-L2, resulting in enhanced T-cell proliferation and interferon-gamma (IFN- $\gamma$ ) release in vitro. Nivolumab binds with high affinity to activated human T-cells expressing cell surface PD-1 and to cynomolgus monkey PD-1.2 In a mixed lymphocyte reaction (MLR), nivolumab promoted a reproducible concentration-dependent enhancement of IFN- $\gamma$  release. In intravenous (IV) repeat-dose toxicology studies in cynomolgus monkeys, nivolumab was well tolerated at doses up to 50 mg/kg, administered weekly for 5 weeks, and at doses up to 50 mg/kg, administered twice weekly for 27 doses. While nivolumab alone was well tolerated in cynomolgus monkeys, combination studies have highlighted the potential for enhanced toxicity when combined with other immunostimulatory agents.

In addition, an enhanced pre- and postnatal development (ePPND) study in pregnant cynomolgus monkeys with nivolumab was conducted. Administration of nivolumab at up to 50 mg/kg 2QW was well tolerated by pregnant monkeys; however, nivolumab was determined to be a selective developmental toxicant when administered from the period of organogenesis to parturition at  $\geq 10$  mg/kg (area under the concentration-time curve [AUC] from time zero to 168 hours [AUC(0-168 h)] 117,000  $\mu\text{g}\cdot\text{h}/\text{mL}$ ). Specifically, increased developmental mortality (including late gestational fetal losses and extreme prematurity with associated neonatal mortality) was noted in the absence of overt maternal toxicity. There were no nivolumab-related changes in surviving infants tested throughout the 6-month postnatal period. Although the cause of these pregnancy failures was undetermined, nivolumab-related effects on pregnancy maintenance are consistent with the established role of PD-L1 in maintaining fetomaternal tolerance in mice.

### 1.5.3. Effects in Humans

The pharmacokinetics (PK), clinical activity, and safety of nivolumab have been assessed in subjects with non-small cell lung cancer (NSCLC), melanoma, clear-cell renal cell carcinoma (RCC), classical Hodgkin Lymphoma (cHL), urothelial carcinoma (UC), squamous cell carcinoma of the head and neck (SCCHN), in addition to other tumor types. Nivolumab monotherapy is approved in multiple regions, including the US and EU, for unresectable or metastatic melanoma, previously treated metastatic NSCLC, previously treated advanced RCC, previously treated relapsed or refractory cHL, and previously treated advanced or metastatic UC; it is also approved for the treatment of previously treated recurrent or metastatic SCCHN in the US. In addition, nivolumab has been approved for use in combination with ipilimumab for unresectable melanoma in multiple countries, including the US and EU. Nivolumab is being investigated both as monotherapy and in combination with chemotherapy, targeted therapies, and other immunotherapies for the treatment of several types of cancer.

### 1.5.4. Clinical Pharmacokinetics

The PK of nivolumab was studied in subjects with cancer over a dose range of 0.1 to 20 mg/kg administered as a single dose or as multiple doses of nivolumab every 2 or 3 weeks. Nivolumab clearance (CL) decreases over time, with a mean maximal reduction (% coefficient of variation [CV%]) from baseline values of approximately 24.5% (47.6%) resulting in a geometric mean steady state clearance (CLss) (CV%) of 8.2 mL/h (53.9%); the decrease in CLss is not considered clinically relevant. The geometric mean volume of distribution at steady state (Vss) was 6.8 L (27.3%), and geometric mean elimination half-life (t1/2) was 25 days (77.5%). Steady-state concentrations of nivolumab were reached by 12 weeks when administered at 3 mg/kg Q2W, and systemic accumulation was approximately 3.7-fold. The exposure to nivolumab increased dose proportionally over the dose range of 0.1 to 10 mg/kg administered every 2 weeks. Additionally, nivolumab has a low potential for drug-drug interactions. The clearance of nivolumab increased with increasing body weight. The PPK analysis suggested that the following factors had no clinically important effect on the CL of nivolumab: age (29 to 87 years), gender, race, baseline LDH, PD-L1 status, solid tumor type, baseline tumor size, and hepatic impairment. Although ECOG status, baseline glomerular filtration rate (GFR), albumin, and body weight had an effect on nivolumab CL, the effect was not clinically meaningful. PPK analysis suggest that nivolumab CL in subjects with cHL was approximately 32% lower relative to subjects with NSCLC; however, the lower CL in cHL subjects was not considered to be clinically relevant as nivolumab exposure was not a significant predictor for safety risks for these patients. When nivolumab is administered in combination with ipilimumab, the CL of nivolumab was increased by 29%, whereas there was no effect on the clearance of ipilimumab. PPK and exposure response analyses have been performed to support use of nivolumab 240 mg Q2W, 360 mg Q3W, and 480 mg Q4W dosing regimens in subjects with cancer in addition to the 3 mg/kg Q2W regimen. A flat dose of nivolumab 240 mg Q2W was selected since it is identical to a dose of 3 mg/kg for subjects weighing 80 kg, the observed median body weight in nivolumab treated cancer patients, while the nivolumab 360 mg Q3W and 480 mg Q4W regimens allow flexibility of dosing with less frequent visits and in combination with other agents using alternative dosing schedules to Q2W. Using a PPK model, the overall distributions of nivolumab exposures (Cavgss, Cminss, Cmaxss, and Cmin1) are comparable after treatment with either nivolumab 3 mg/kg or 240 mg Q2W. Following nivolumab 360 mg Q3W and 480 mg Q4W, Cavgss are expected to be similar to those following nivolumab 3 mg/kg or 240 mg Q2W, while Cminss are predicted to be 6% and ~16% lower, respectively, and are not considered to be clinically relevant. Following nivolumab 360 mg Q3W and 480 mg Q4W, Cmaxss are predicted to be approximately ~23% and ~43% greater, respectively, relative to that following nivolumab 3 mg/kg Q2W dosing. However, the range of nivolumab exposures (median and 90% prediction intervals) following administration of 240 mg flat Q2W, 360 mg Q3W, and 480 mg Q4W regimens across the 35 to 160 kg weight range are predicted to be maintained well below the corresponding exposures observed with the well tolerated 10 mg/kg nivolumab Q2W dosing regimen. In this study we will use the flat dose of 360mg Q3W. Although this is a less frequent dosing regimen, it will

allow combination of nivolumab with the capecitabine schedule. This nivolumab dosing regimen was selected using several simulation models to provide approximately equivalent exposures following administration of nivo 3 mg/kg Q2W. The models predicted that following administration of nivo 360 mg Q3W exposures are expected to be similar to those following nivo 3 mg/kg or 240 mg Q2W.

#### 1.5.5. Clinical Efficacy

Nivolumab has demonstrated durable responses exceeding 6 months as monotherapy and in combination with ipilimumab in several tumor types, including NSCLC, melanoma, RCC, cHL, SCLC, gastric cancer, SCCHN, urothelial cancer, HCC, and CRC. In confirmatory trials, nivolumab as monotherapy demonstrated a statistically significant improvement in OS as compared with the current standard of care in subjects with advanced or metastatic NSCLC, unresectable or metastatic melanoma, advanced RCC, or SCCHN. Nivolumab in combination with ipilimumab improved PFS and ORR over ipilimumab alone in subjects with unresectable or metastatic melanoma.

#### 1.5.6. Clinical Safety

The overall safety experience with nivolumab, as a monotherapy or in combination with other therapeutics, is based on experience in approximately 16,900 subjects treated to date. For monotherapy, the safety profile is similar across tumor types. There is no pattern in the incidence, severity, or causality of AEs to nivolumab dose level. In Phase 3 controlled studies, the safety profile of nivolumab monotherapy is acceptable in the context of the observed clinical efficacy, and manageable using established safety guidelines. Clinically relevant AEs typical of stimulation of the immune system were infrequent and manageable by delaying or stopping nivolumab treatment and timely immunosuppressive therapy or other supportive care. Based on preliminary data from an ongoing Phase 1 study, there have been no unexpected safety findings to date in patients with sepsis who received a single dose of nivolumab monotherapy. In several ongoing clinical trials, the safety of nivolumab in combination with other therapeutics such as ipilimumab, cytotoxic chemotherapy, anti-angiogenics, and targeted therapies is being explored. Most studies are ongoing and, as such, the safety profile of nivolumab combinations continues to evolve. The most advanced combination under development is nivolumab + ipilimumab, which is approved in subjects with unresectable or metastatic melanoma, and being studied in multiple tumor types. Results to date suggest that the safety profile of nivolumab+ipilimumab combination therapy is consistent with the mechanisms of action of nivolumab and ipilimumab. The nature of the AEs is similar to that observed with either agent used as monotherapy; however, both frequency and severity of most AEs are increased with the combination. Nivolumab at 360mg q3w has been shown to be safe in combination with capecitabine and oxaliplatin in patients with G/GEJ cancers (Kang YK, et al. Annals of Oncology 2017).

There are other ongoing studies evaluating the combination of capecitabine and nivolumab (NCT02746796; NCT03006705).

## **1.6 Patient reported outcomes (PRO)**

The assessment of patient-reported outcomes (PROs) in clinical research provides important insight into how therapies impact the daily lives of patients. Patient reports regarding health related quality of life have proven more comprehensive than provider-collected data in breast cancer patients ([Oberguggenberger et al 2011](#)).

### **1.6.1 EORTC QLQ-C30**

In this study patient-reported disease related symptoms and health-related quality of life (HRQoL) will be evaluated using the validated EORTC QLQ-C30 questionnaire. The EORTC QLQ-C30 questionnaire was developed to assess HRQoL and is the most commonly used cancer-specific tool in oncology.

The EORTC QLQ-C30 comprises 30 questions designed for all cancer types. Questions can be grouped into the following scales:

- 5 multi-item functional scales (physical, role, emotional, cognitive and social)
- 3 multi-item symptom scales (fatigue, pain, nausea vomiting)
- A 2-item global QoL scale
- 5 single items assessing the following common cancer symptoms: dyspnea, loss of appetite, insomnia, constipation, diarrhea
- 1 item on the financial impact of the disease.

All the EORTC scales range from 0 to 100 (through transformation of scores). A high scale score represents a higher response level. Thus a high score for a functional scale represents a high / healthy level of functioning, while a high score for a symptom scale / item represents a high level of symptomatology / problems.

### **1.6.2 Administration of PRO questionnaires**

Paper-based EORTC QLQ-C30 will be administered at screening (prior to randomization), at 6 weeks visit and at the end of treatment.

Each center must allocate the responsibility for the administration of the questionnaires to a specific individual (e.g., a research nurse, study coordinator) and if possible assign a back-up person to cover if that individual is absent. The significance and relevance of the data need to be explained carefully to participating patients so that they are motivated to comply with data collection.

The instructions for completion of the PRO questionnaires are as follows:

- They must be completed prior to any other study procedures (following informed consent) and before discussion of disease progress to avoid biasing the patient's responses to the questions. They must be completed in private by the patient
- The patient should be given sufficient time to complete at their own speed
- The patient should not receive help from relatives, friends or clinic staff to answer the questionnaire.
- On completion of the questionnaire it should be handed back to the person responsible for questionnaires who should check for completeness

- Only one answer should be recorded for each question

### **1.7. Rationale for Current Study**

Recent results presented at ASCO 2017 indicated that a subset of patients with early stage triple negative breast cancer benefit from immune checkpoint inhibitors. It is of critical importance to develop tools to help identify which patients benefit from this strategy. As discussed above, we currently don't have any validated biomarker that allow us to detect this subset of patients. Tumor biopsies at different timepoints are not an option in this population when the only tumor available is the residual tissue removed at the time of surgery. The presence of circulating tumor cells after chemotherapy has been shown to have a negative impact on DFS and OS (Rack B, et al. JNCI 2014) but has not been used to predict benefit from immunotherapy. The presence of PD-L1 expression on tumor cells has been associated with objective responses in metastatic cancer (Topalian, NEJM) but not been evaluated in patients who have completed adjuvant therapy. Presence of TILs has been associated with increased PD-L1 infiltrate, but the association between increased TILs and response to immune checkpoint therapy has not yet been established. For this pilot study, we selected the refined peripheral immunoscore (PIS) defined by Farsaci based on it's being the closest to the particular scenario proposed on this study. His group demonstrated that an immunoscore of refined immune cell subsets showed significant prognostic value in PFS for metastatic breast cancer patients receiving docetaxel plus vaccine ( $P < 0.001$ ) and for metastatic prostate cancer patients receiving radionuclide plus vaccine ( $p=0.004$ ), but not on the same groups when treated with chemotherapy alone.

This pilot study will provide preliminary data regarding the role of PIS in predicting the benefit of immune checkpoint inhibition with or without chemotherapy for high risk patients with TNBC and residual disease after effective neoadjuvant chemotherapy. If the peripheral immunoscore fails as a biomarker, this pilot study would still be very relevant as we will be collecting other exploratory biomarkers in this unique population.

## **2.0 STUDY OBJECTIVES**

### 2.1 Primary objective:

- 1) To assess the immunologic effects of capecitabine, nivolumab or the combo, post neoadjuvant and post-surgery, in the adjuvant setting, in patients with high risk TNBC as defined by presence of residual disease (breast and or LNs) at surgery, in terms of the change of PIS.
  - a) We hypothesized that among patients with TNBC and residual disease at the time of surgery, the change of the Peripheral ImmunoScore (PIS) from baseline to week 6 will be higher among those who receive post-surgery immunotherapy (ARM A and C), compared to those who receive post-surgery chemotherapy alone (ARM B).

### 2.2 Secondary objectives:

- 1). To determine the incidence of toxicity graded using the National Cancer Institute CTCAE v. 4.0 until 30 days after last dose of treatment on trial.
- 2). To determine association between changes in PIS from baseline to week 6 and week 12 and clinical outcome variables (DRFS and OS at 2-years)). After end of study visit, clinical follow up or telephone communication every 3months.
- 3). To describe the following endpoints and compare them between arms: DRFS, OS
- 4) Translational endpoints:
  - a) Circulating-tumor DNA (ct-DNA)

### Exploratory objectives:

- c) To describe the immune contexture in residual tumors of patients with high risk TNBC after receiving neoadjuvant chemotherapy
- d) Tissue banking for future studies (NGS of initial biopsy and surgical specimen)
- e) To explore the impact of nivolumab on patient-reported outcomes (PROs) of health-related quality of life (HRQoL), as measured by the European Organization for Research and Treatment of Cancer (EORTC) EORTC Quality of Life Questionnaire Core 30 (QLQ-C30) disease related multi-item symptom and functional scales.

### 3.0 STUDY DESIGN

[figure not shown]

Figure 3. Study design

The OXEL “Opdivo, XELoda or combination therapy as adjuvant therapy for triple negative breast cancer with residual disease following neoadjuvant chemotherapy” is a pilot phase II open-label three arm randomized trial of nivolumab, capecitabine or combination as adjuvant therapy for 45 patients with residual TNBC after adequate neoadjuvant chemotherapy followed by definitive surgery. We will enroll 15 patients per arm (45 totally for 3 arms).

Patients are randomly assigned to 1 of 3 treatment arms:

- ARM A – Nivolumab 360 mg iv q3weeks for x 6 cycles;
- ARM B - Capecitabine 1250mg/m^2 bid D1-D14 q3 weeks x 6 cycles;
- ARM C - Nivolumab 360mg iv q3weeks + Capecitabine 1250mg/m^2 bid D1-D14 q3 weeks x 6 cycles.

Nivolumab (Opdivo®) is a human programmed death receptor-1 (PD-1) antibody currently approved in different diseases. Capecitabine (Xeloda®) was selected for ARM B (as contemporary control arm) given the recent results from CREATE-X trial and the increasing use by the community (feasibility). Importantly, available data from other scenarios indicates that capecitabine does not have immunosuppressive effects. Given capecitabine low myelosuppressive potential, it was felt to be a reasonable chemotherapy partner with the checkpoint inhibitor in this setting (ARM C). Finally, there is safety data regarding combination of nivolumab and capecitabine in patients with G/GEJ tumors (Kang YK, et al. Annals of Oncology 2017).

## **4.0 SUBJECT POPULATION**

### **4.1 Subject Population, Number of Subjects and Feasibility**

#### **4.1.1 Subject Population**

Patients will have triple negative breast cancer. Enrolled patients will have completed standard neoadjuvant chemotherapy and will have residual disease at the time of definitive breast surgery. Patients will have completed adequate local therapy.

#### **4.1.2 Number of Subjects**

45 patients will be enrolled with advanced triple negative breast cancer. Patients who don't have evaluable samples as per protocol will be replaced.

### **4.2 Inclusion Criteria**

#### **1. Biopsy proven TNBC:**

- ER- and PR- defined as  $\leq 5\%$  cells stain positive
- HER2 negativity defined as:
  - IHC 0, 1+ without in situ hybridization (ISH) HER2/neu chromosome 17 ratio OR
  - IHC 2+ and ISH HER2/neu chromosome 17 ratio non-amplified with ratio less than 2.0 and if reported average HER2 copy number  $< 6$  signals/cells

2. Residual disease of 1.0 cm at least of the primary tumor and/or node positive disease (at least ypN1) and/or Residual Cancer Burden (RBC) classification II or III. Tissue availability needs to be confirmed and should be received by the lead institution by day 1 of study treatment. (Note: As long as tissue sample is confirmed shipped, the subject will be eligible)

3. Patients must have completed neoadjuvant chemotherapy; patients must NOT have received capecitabine as part of their neoadjuvant therapy regimen. Acceptable preoperative regimens include an anthracycline or a taxane, or both. Participants who received preoperative therapy as part of a clinical trial may enroll. Participants may not have received adjuvant chemotherapy after surgery prior to randomization. Carboplatin-containing neoadjuvant chemotherapy is also allowed). Patients who cannot complete all planned neoadjuvant treatment cycles for any reason are considered high risk and therefore are eligible for the study if they have residual disease.

4. Recovery of all toxicities from previous therapies to at least grade 1, except alopecia and  $\leq$  grade 2 neuropathy which are allowed.

5. Must have completed definitive resection of primary tumor and have no evidence of unresected or metastatic disease at the time of study entry. For those who don't require radiotherapy, the most recent surgery for breast cancer must have been completed at least 14 days prior to day 1 of study treatment, but no more than 84 days prior to study registration.

- Negative margins for both invasive and ductal carcinoma in situ (DCIS) are desirable,

however patients with positive margins may enroll if the treatment team believes no further surgery is possible and patient has received radiotherapy; patients with margins positive for lobular carcinoma in situ (LCIS) are eligible

- Either mastectomy or breast conserving surgery (including lumpectomy or partial mastectomy) is acceptable
- Sentinel node biopsy post neoadjuvant chemotherapy (i.e. at the time of definitive surgery) is allowed; axillary dissection is encouraged in patients with lymph node involvement, but is not mandatory
- Whole breast radiotherapy is required for participants who underwent breast-conserving therapy, including lumpectomy or partial mastectomy. Participants must have completed radiotherapy at least 14 days prior (but no more than 84 days prior) to day 1 of study treatment.
- Post-mastectomy radiotherapy is required for all participants with a primary tumor  $\geq 5$  cm or involvement of  $\geq 4$  lymph nodes. For participants with primary tumors  $< 5$  cm or with  $< 4$  involved lymph nodes, provision of post-mastectomy radiotherapy is at the discretion of the treating physician.

#### 6. ECOG PS 0-1

7. Patients must not be planning to receive concomitantly other biologic therapy, hormonal therapy, other chemotherapy, surgery, radiation therapy or other anti-cancer therapy while receiving treatment on this protocol.

8. At the time of registration (randomization), patients must have the following laboratory results (obtained within 28 days prior to registration):

- a. A serum TSH prior to registration to obtain a baseline value.
- b. Patients must have adequate bone marrow function as evidenced by all of the following:
  - ANC  $\geq 1,500$  microliter (mcL);
  - Platelets  $\geq 100,000$ /mcL;
  - Hemoglobin  $\geq 9$  g/dL.
- c. Patients must have adequate hepatic function as evidenced by the following:
  - Total bilirubin  $\leq 1.5$  x institutional upper limit of normal (IULN) (except Gilbert's Syndrome, who must have a total bilirubin  $< 3.0$  mg/dL), and
  - SGOT (AST) or SGPT (ALT) and alkaline phosphatase  $\leq 2.5$  x IULN.
- d. Patients must have adequate renal function as evidenced by ONE of the following:
  - Serum creatinine  $\leq$  IULN OR
  - Measured or calculated creatinine clearance  $\geq 60$  mL/min.
- e. Normal thyroid function or stable on hormone supplementation (Patients that meet the definition of asymptomatic subclinical hypothyroidism will be eligible to participate)
- f. Women of childbearing potential (WOCBP) must have a negative urine or serum pregnancy test within 28 days prior to registration and within 24h prior to the start of nivolumab. In addition, women of childbearing potential must agree to have a pregnancy test every 4 weeks while on nivolumab.

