### **4.3 Exclusion criteria**

1. Stage IV disease
2. Receipt of adjuvant chemotherapy
3. Diagnosis of other invasive cancer except for adequately treated cervix cancer or skin cancer, or more than 5 years since other diagnosis of invasive cancer without current evidence of disease
4. Previous exposure to capecitabine, fluorouracil or immunotherapy with anti-PD1, anti-PDL1, anti-CTLA4 or similar drugs.
5. Active autoimmune disease that has required systemic treatment in the past 2 years; replacement therapy is not considered a form of systemic therapy. Autoimmune diseases include but are not limited to myasthenia gravis, myositis, autoimmune hepatitis, systemic lupus erythematosus, rheumatoid arthritis, inflammatory bowel disease, vascular thrombosis associated with antiphospholipid syndrome, Wegener's granulomatosis, Sjogren's syndrome, Guillain-Barre syndrome, multiple sclerosis, vasculitis or glomerulonephritis.
6. TB, active hepatitis B (defined as having a positive hepatitis B surface antigen [HBsAg]), active hepatitis C (defined as positive test for hepatitis C viral load by polymerase chain reaction [PCR]) or other active infection. Patients with past hepatitis B virus (HBV) infection or resolved HBV infection (defined as having a negative HBsAg test and a positive antibody to hepatitis B core antigen [anti-HBc] antibody test) are eligible. Patients with positive hepatitis C antibody and negative quantitative hepatitis C by PCR are eligible. Patients who have completed curative therapy for HCV are eligible. Patients with known HIV infection are eligible if they meet each of the following 3 criteria: CD4 counts  $\geq$  350 mm^3; serum HIV viral load of < 25,000 IU/ml and treated on a stable antiretroviral regimen.
7. History of (non-infectious) pneumonitis that required steroids or evidence of active pneumonia
8. Uncontrolled disease
9. Chronic use of systemic steroids
10. Live vaccine within 30 days prior to registration.
11. Incapacity to provide consent or to follow clinical trial procedures
12. Pregnancy, lactation, or planning to be pregnant

Patients with microsatellite unstable tumors will not be excluded as immunotherapy as adjuvant therapy is not standard for these patients but we will prospective collect this data.

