#### 4.6.1 Screen Failures

Patients will be identified and enrolled after completing definitive breast surgery. All patients must continue to meet the inclusion and exclusion criteria up to and including the first day of treatment. Reasons for patients who have enrolled, but become ineligible could include (but are not limited to):

- The patient is no longer eligible based on laboratory parameters
- The patient's performance status has declined
- The patient does not have adequate tissue for initial assessment

Patients who become ineligible prior to initiation of therapy per protocol will be considered screen failures. Screen failures must be replaced until 45 patients with advanced triple negative breast cancer are enrolled.

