### 5.3. Capecitabine

Capecitabine will be given at 1250 mg/m^2 PO BID for Days 1-14 only of a 21-day cycle for 6 cycles.

Commercially available capecitabine will be used. Locally obtained commercial supplies of capecitabine will be used in accordance with local regulations. As capecitabine is an oral drug available in fixed doses, the dose administered may not exactly match the calculated dose. Determination of the rounding of capecitabine doses for administration should be made according to local institutional practices, with documentation of both the calculated and administered dose. Per package insert, it is recommended that capecitabine be administered with food. Capecitabine should be stored according to the package insert. For capecitabine, the package insert and local standard of care rules for dose reduction should also be applied. Dose modifications will be documented.

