## 6.0 STUDY PROCEDURES AND TREATMENT ASSIGNMENT

### 6.1. Table of events

	Pre-registration	Screening	On Study (maximum 6 cycles; cycle is every 21 d)	Treatment discontinuation	Surveillance
	Post-surgery	-30 days	D1 of each cycle +/- 7 days. Each cycle is 21 days.	30 days (+/-7 days) after last dose	
Assessments					
Informed consent	X				
Medical history and height		X			
Physical examination		X	X ^	X	
Weight, BP		X	X ^	X	
ECOG PS		X	X ^	X	
CMP		X	X	X	
Creatinine clearance		X	X	X	
CBC with differential		X	X	X	
Breast imaging (remaining tissue only)					Yearly +/- 30 days
Adverse event and con meds assessment		X	X ^		
Urine pregnancy or serum HCG for WOCBP only		X	X ^ (every 3 weeks) for Arm A and C		
ACTH and Thyroid Function Tests#		X	X ^ (week 12) for Arm A and C	X	
Hepatitis and HIV screening*		X			
EORTC QLQ-C30 &		X	X (week 6)	X	
Telephone communication or focused physical exam+					Every 3-6 months
Treatment					
			Nivolumab 360mg iv q3w; capecitabine 1250mg/m  D1-14		

Correlative Samples					
Tumor from initial diagnosis		X (if available)			
Tumor from definitive surgery – with IHC testing for MSI	X				
Serum for peripheral immunoscore			X ^ (baseline, week 6 and 12)	X (if recurrence)	
Blood for ct-DNA \$			X ^ \$ (baseline, week 6 and 12)	X (if recurrence)	
Tumor from metastatic site				X (if recurrence)	

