## **6.3. Screening**

Within 30 days of study registration:

- Complete medical history and complete physical examination including: height, weight, BP and ECOG performance status
- Complete metabolic profile including serum chemistries and electrolytes
- Calculated creatinine clearance
- Complete blood count with differential
- Urine pregnancy test or serum HCG (only in women of child bearing potential, WOCBP) within 24 hours prior to the start of nivolumab. Women should be counseled regarding acceptable birth control methods to utilize from the time of screening to start treatment. In addition, women of child bearing potential must accept to have a pregnancy test every 3 weeks if they are randomized to a nivolumab arm.
- Adverse event and concomitant medication assessment

- EORTC QLQ-C30 should be completed during screening
- Obtain tumor from definitive breast surgery (mandatory) and from initial biopsy (if tissue is available) and send to the main site (Georgetown). See lab manual for more details.

**Note:** Assessments performed for clinical indications (not exclusively to determine study eligibility) may be used for screening/baseline values even if the studies were done before informed consent was obtained.

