#### **6.5. On Study Day 1**

Cycle 1 Day 1 testing need not to be repeated if completed within 14 days of starting therapy. Will be obtained blood samples for correlative studies (see Correlative Laboratory Manual for more details). Cycle 1 Day 1 must occur within 2 weeks after receiving randomization results.

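### Arm B women of childbearing potential have no scheduled pregnancy test after the registration test, although pregnancy bars and stops treatment in every arm

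*Combined protocol and SAP*

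**What the plan says.** The rules about pregnancy apply to every arm:

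- Section 4.3, item 12 excludes "Pregnancy, lactation, or planning to be pregnant".
- Section 4.6.1 states: "All patients must continue to meet the inclusion and exclusion criteria up to and including the first day of treatment".
- Section 6.7 takes a participant who becomes pregnant off protocol therapy, whatever her arm.
- Section 4.4.3 requires contraception until 6 months after the last dose and names capecitabine alongside nivolumab.

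The rules about testing for pregnancy do not:

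- Section 4.2, item 8f requires a negative test no more than 28 days before registration in all women of childbearing potential. It then requires a second test "within 24h prior to the start of nivolumab", and repeat tests only while the woman is on nivolumab.
- Section 6.3 times the pre-dose test to nivolumab in the same way, and asks for a "pregnancy test every 3 weeks if they are randomized to a nivolumab arm".
- In the table of events (6.1), the screening test is not limited by arm, but the on-study entry is "every 3 weeks) for Arm A and C". The treatment-discontinuation and surveillance columns of that row are empty.

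**The concern.** Arm B takes capecitabine without nivolumab, so an instruction triggered by starting or receiving nivolumab never reaches it. The protocol sets an all-arm exclusion, an all-arm eligibility check on the first treatment day and an all-arm stopping rule, but gives Arm B no scheduled step after registration that would show whether any of them has been met.

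A pregnancy that begins after the registration test could therefore be found late, during cytotoxic dosing. Arm C takes the same capecitabine regimen and is tested, so the drug does not explain the difference. Section 6.7 works once a pregnancy is known; what Arm B lacks is a planned means of finding it.

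**Working it through.** The plan states no figure on this point, so there is none to reproduce. The check has two parts.

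**Could any other provision supply an Arm B test?**

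- Section 5.0 has Arm B drug handled like standard-of-care medication. It covers supply, dosing by actual weight and dose adjustment, and schedules no pregnancy test.
- Section 6.5 says "Cycle 1 Day 1 testing need not to be repeated if completed within 14 days of starting therapy". This tells the site when a Day 1 test may be skipped, not which tests are due. The on-study pregnancy row in 6.1 names only Arms A and C.
- Section 4.6.1 requires eligibility to persist to Day 1 but names no test to confirm it.
- Section 7.5 acts only after a pregnancy is discovered, and it concerns the investigational product; the synopsis lists nivolumab alone as investigational. For Arm B the stopping rule rests on 6.7.

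None of these schedules a test in Arm B after the registration test.

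**How old can the last scheduled negative test be in Arm B?**

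Inputs:

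- Registration test: up to 28 days before registration (8f). Item 8 treats registration and randomization as the same event.
- Randomization to first dose: up to 14 days, since "Cycle 1 Day 1 must occur within 2 weeks after receiving randomization results" (6.5).
- Capecitabine schedule: "PO BID for Days 1-14 only of a 21-day cycle for 6 cycles" (5.3).

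Steps:

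1. Age at first dose = 28 + 14 = **42 days**.
2. Cycle 6 Day 14 falls 5 × 21 + 13 = 118 days after Cycle 1 Day 1.
3. Age at last scheduled dose = 42 + 118 = **160 days**.
4. If a site applied the 14-day provision of 6.5 to this test, the ages become at most 14 days at first dose and 14 + 118 = **132 days** at the last, still with no on-treatment test.

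By comparison, women in Arms A and C have a test within 24 hours of their first nivolumab dose and then nominally every 21 days (6.1, 6.3) or every 28 days (8f).

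**Tests needed to close the gap:** one before the first dose plus one at each of cycles 2 to 6 makes 6 per woman. If all 15 Arm B patients were of childbearing potential, that is 15 × 6 = 90 tests, before counting any replaced patients.

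**The case against.** The strongest reply is that this is a consistent choice and not a slip. All three places that set testing tie it to nivolumab, the only investigational agent. The ACTH and thyroid tests on treatment are limited to Arms A and C in the same way. Section 1.5.2 gives developmental-toxicity data for nivolumab only, and Arm B is a contemporary control whose drug is managed like routine care. Other protections also apply in every arm: a negative test before registration, contraception counselling, contraception through 6 months after capecitabine, cycle visits with examination and adverse-event review, and 24-hour reporting of pregnancies. Sites may test locally in any case.

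The consistency is real, but it does not remove the mismatch. The endocrine tests follow effects that section 7.3 attributes to nivolumab, whereas the pregnancy exclusion, stopping rule and contraception requirement cover capecitabine too. Local testing may happen, but the protocol does not require it.

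Three parts of the objection stand:

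- The safeguards lower the risk, and the documents give no pregnancy rate and no count of women of childbearing potential in Arm B. The figures measure the age of a test, not the chance of an exposed pregnancy.
- The 160 days assumes a course without delays. Visit windows of 7 days and holds of up to 42 days, or longer with approval, could lengthen it. The screening window is also 30 days in 6.1 and 6.3, against 28 in 8f; the 28 was used here.
- Sample size, power and the analysis of the primary endpoint are unaffected.

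**Conclusion.** The concern holds. As written, a woman of childbearing potential in Arm B has one protocol-scheduled pregnancy test, before registration, and none before or during six cycles of capecitabine. With the pre-treatment windows used in full, that test is 42 days old at the first dose; with treatment on schedule, it is 160 days old at the last. On the reading of 6.5 most favourable to the plan, the figures are 14 and 132 days. This is a participant-safety gap in an unknown subset of 15 patients, reduced by the contraception and visit requirements, and it should be corrected because doing so is cheap. The documents do not say whether Arm B dosing is complete; the change helps only women still to be treated.

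**What to change.** - In 4.2 (item 8f) and 6.3, time the pre-dose test to the start of study treatment instead of the start of nivolumab, and list that test under 6.5 as a Day 1 check for all arms.
- In 6.1, extend the on-treatment pregnancy row to Arm B at its existing cycle visits. Reword 8f and 6.3 so that repeat testing applies to any study treatment.
- While 8f is open, settle on one interval. It says every 4 weeks where 6.1 and 6.3 say every 3; every 3 weeks matches the cycle visits.

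The cost is wording in four places and at most 6 routine urine or serum tests per woman (90 across 15 patients), at visits Arm B already attends for blood counts and chemistry. Section 10.1 requires IRB approval of the amendment before it takes effect, and the consent form may need a matching line.
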